Sample size estimation: Referring to delayed language development in children as the disease outcome, the incidence rate (p_1) of delayed language development in the group exposed to high prenatal sugar is 15%, and the relative risk (RR) is 2.0, with a desired significance level (α) of 0.05 and a desired power ($1-\beta$) of 0.90. By plugging in these values into

the formula, it is determined that both the exposed group and the control group require 160 individuals. Considering the possibility of loss to follow-up, the sample size is increased by 10%. The final estimated sample size for the cohort is 356 cases, with a planned investigation of 360 individuals in the blood sugar abnormality specialized disease cohort.

The sample calculation formula for the cohort study collects data information through the electronic medical record system and the Western Children's Health and Disease Cohort Platform, with dual data entry into an Excel database. Differences in the distribution of general conditions of pregnant women are compared using statistical methods such as the chi-square test or Fisher's exact probability test for categorical data (Socio demographic profile, menstrual and reproductive history, indoor environment Environmental factors, Scale indicators etc.), and statistical methods such as the t-test or ANOVA test for continuous data (Check labs (e.g., fasting blood glucose, glycosylated hemoglobin, lipids, liver and kidney function, etc.). After further controlling for confounding factors, logistic regression analysis is used to explore the impact of poor blood sugar management (high prenatal sugar exposure) on delayed language development around 1-2 years of age.

The combined effect of GDM and postnatal environment of the offspring was analyzed using an EXCEL spreadsheet developed by Andersson et al. The additive interaction was evaluated using three indices: relative excess risk due to interaction (RERI), attributable proportion due to interaction (AP), and synergy index (S). If the 95% confidence intervals (CI) of RERI and AP included 0, and the 95% CI of S included 1, it indicated no additive interaction; otherwise, there was an additive interaction.

The regression models were used to screen the effect of maternal GDM and related factors on the delayed language development (DLD) in

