offspring. The binomial logistics regression model and the lasso regression model were constructed by using the "rms" and "glmnet" package to analyse risk factors. The nomogram, which based on proportionally converting each regression coefficient to a zero to one-hundred-point scale, was used to screen the effect of maternal GDM and related factors on the DLD. The effect of the variable with the highest β coefficient was assigned one hundred points. The points were added across independent variables to derive total points, which were converted to predicted probabilities. The total scores of each patient were calculated based on the nomogram for clinical prediction. We used the predictive performance of the nomogram was measured by concordance index (C index). Prediction models were validated by plotting calibration curves and using bootstrap method with one thousand replicate samples. The clinical validity of the prediction model was evaluated using decision curve analysis (DCA).

All analyses were performed using SPSS software (SPSS Inc., Chicago, IL, USA, version 21.0) and R version (4.1.3, <http://www.r-project.org/>). The significance level for statistical tests is set at a value of 0.05, the selection criterion for the regression equation is set at a level of 0.05, and the exclusion level is set at 0.10. Missing values are handled according to the default method in SPSS, which means that observations with missing values in the test variables are excluded from the analysis. A p-value of <0.05 indicates a statistically significant difference.

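### The plan does not say which effect measure feeds RERI, AP and S; if the odds ratios from its logistic models are used, the no-interaction values no longer mean that risks add.

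*Protocol*

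**What the plan says.** The paragraph on the combined effect of GDM and the offspring's postnatal environment uses a published Excel spreadsheet and reads: "The additive interaction was evaluated using three indices: relative excess risk due to interaction (RERI", followed by the attributable proportion (AP) and the synergy index (S). If the 95% intervals for RERI and AP include 0 and the interval for S includes 1, "it indicated no additive interaction; otherwise, there was an additive interaction". Any one of the three intervals missing its null value is therefore enough to declare interaction. The paragraph does not say whether risk ratios or odds ratios go into the spreadsheet.

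Elsewhere, the adjusted analysis of the main exposure is logistic: "logistic regression analysis is used to explore the impact of poor blood sugar management". For risk factors and the nomogram, "The binomial logistics regression model and the lasso regression model were constructed". No log-binomial, Poisson or risk-difference model is named.

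The sample-size paragraph puts the incidence of delayed language development "in the group exposed to high prenatal sugar is 15%, and the relative risk (RR) is 2.0".

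**The concern.** RERI, AP and S ask whether the excess risks from two factors add up. RERI = 0, AP = 0 and S = 1 correspond to additive risks when the inputs are risk ratios. Odds ratios serve as substitutes only when the outcome is rare in all four exposure groups, which the plan's own incidence rules out.

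This differs from the familiar remark that an odds ratio exaggerates a risk ratio. Here the reference value of a yes/no decision moves. A study in which GDM and a poor environment contribute independently and additively could be reported as showing synergy. The project title joins blood sugar management and the nurturing environment, so the combined effect is not a side question.

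**Working it through.** **1. How common is the outcome?** Inputs from the sample-size paragraph: 15%, RR 2.0, α 0.05, power 0.90, 160 per group.

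n = [1.96·√(2p̄q̄) + 1.2816·√(p₁q₁ + p₂q₂)]² / (p₂ − p₁)²

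- 15% vs 30% (p̄ = 0.225): (1.96 × 0.5906 + 1.2816 × 0.5809)² / 0.0225 = 3.617 / 0.0225 ≈ 161. This matches 160, and 320 / 0.90 = 356 matches the stated total.
- 7.5% vs 15%, the literal reading with 15% in the exposed group: 371 per group two-sided, 303 one-sided. Neither matches.

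The sizing therefore rests on 15% and 30%. Both readings are carried forward.

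**2. The null on the odds-ratio scale.** With risks listed as neither / GDM only / environment only / both:

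RERI = OR₁₁ − OR₁₀ − OR₀₁ + 1; AP = RERI / OR₁₁; S = (OR₁₁ − 1) / (OR₁₀ + OR₀₁ − 2)

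- 15/30/30/45% is exactly additive. Odds are 0.1765, 0.4286, 0.4286 and 0.8182, so the ORs are 2.429, 2.429 and 4.636. RERI = 4.636 − 4.857 + 1 = 0.78; AP = 0.779 / 4.636 = 0.17; S = 3.636 / 2.857 = 1.27.
- 7.5/15/15/22.5%: ORs 2.176, 2.176 and 3.581. RERI = 0.23, AP = 0.06, S = 1.10.
- With risk ratios, both patterns give exactly 0, 0 and 1.

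**3. How often does the rule err?** Simulation of 320 children, GDM 1:1, four unadjusted cells, delta-method 95% intervals (S on the log scale), 200,000 cohorts per setting. Risks are exactly additive, so every declaration of interaction is false. The environment effect and the prevalence of a poor environment are assumptions, since the document gives neither. Rates are for prevalence 50% / 30%.

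| Risk without / with GDM | Environment effect (points) | RERI, AP, S from ORs | False claims, ORs | False claims, RRs |
|---|---|---|---|---|
| 15 / 30% | 0 | 0, 0, 1 | 7.4 / 7.6% | 6.8 / 6.4% |
| 15 / 30% | 3 | 0.12, 0.04, 1.07 | 8.9 / 9.0% | 7.1 / 6.5% |
| 15 / 30% | 5 | 0.21, 0.07, 1.11 | 9.8 / 10.1% | 7.3 / 6.7% |
| 15 / 30% | 10 | 0.46, 0.12, 1.20 | 12.7 / 13.0% | 7.6 / 6.8% |
| 15 / 30% | 15 | 0.78, 0.17, 1.27 | 16.5 / 16.1% | 7.6 / 6.9% |
| 7.5 / 15% | 3 | 0.08, 0.03, 1.05 | 8.2 / 8.7% | 7.0 / 7.1% |
| 7.5 / 15% | 7.5 | 0.23, 0.06, 1.10 | 9.8 / 10.3% | 7.3 / 7.2% |
| 7.5 / 15% | 15 | 0.53, 0.10, 1.14 | 11.9 / 12.3% | 7.7 / 7.4% |

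A further run with a 2-point effect (14/29/16/31%) gave 8.5-8.8% with odds ratios and 6.6-7.1% with risk ratios.

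**4. Which index drives it?** For 15/30/30/45% at 50% prevalence, the intervals exclude the null in these shares of studies:

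- ORs: RERI 4.1%, AP 16.0%, S 2.6%, any of the three 16.5%.
- RRs: RERI 4.1%, AP 5.0%, S 3.5%, any of the three 7.6%.

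The excess from odds ratios is an AP effect, let through by the any-of-three rule.

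**The case against.** The strongest reply is that the document never ties its logistic models to these indices. Logistic regression is named for the effect of blood sugar management and, with lasso, for risk factors and the nomogram. A cohort sized on a relative risk could supply risk ratios directly. This stands: a reader might infer that the indices can only be built from odds ratios, but that is an inference. The silence still matters, because the decision rule is fixed while its scale is not, and the named models lead to the odds scale.

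The size is also open to challenge. The 16-17% figures need an assumed 15-point environment effect on GDM risks of 15% and 30%. In the 15/30/30/45% example with half the children in a poor environment, the marginal GDM risks are 22.5% and 37.5%, a risk ratio of 1.67 and not the planned 2.0. A pattern that keeps the 15% and 30% margins (7.5/22.5/22.5/37.5%) also gives about 17%, so the environment effect is what counts. With effects of 3 to 5 points, the excess over risk ratios is roughly 1 to 3.5 points. With no effect there is no shift at all. This stands too.

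A reader might also infer that all three indices over-claim. At this sample size they do not: RERI and S each stay below 5%. Nor would risk ratios bring the rule to 5%. The remaining 6-8% comes mainly from accepting any one of three indices.

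Finally, this might be called detail for a separate analysis plan. The document is itself titled a statistical analysis plan, and it fixes both the indices and the decision rule.

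**Conclusion.** The point holds in conditional form. The plan fixes null values that mean additive risks on the risk-ratio scale, leaves the scale unstated, and names only outcome regressions that yield odds ratios. If odds ratios are used and both factors raise risk, the null is displaced upward, exactly and not by sampling error. At about 320 children the false-claim rate is then about 8-17%, against about 6-8% with risk ratios, for assumed environment effects of 2 to 15 points and prevalence of 30-50%.

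The rates also assume a 1:1 GDM split, taken from the sizing, and no covariates. The split is not fully settled, because the plan also describes 360 individuals in the abnormal-blood-sugar cohort. A larger cohort would not cure the problem: at 2,000 children the 15/30/30/45% pattern rises to about 30-37% with odds ratios. That concerns a far larger study than the one planned. The correction should be made before the analysis, although the interaction question did not drive the sample size.

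**What to change.** State that RERI, AP and S are computed from adjusted risk ratios. Two routes are practical:

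- a modified Poisson or log-binomial model with the same covariates and the four GDM-by-environment groups as exposure; or
- risks for those four groups standardised from the logistic model (with the GDM-by-environment product term), with bootstrap intervals.

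R and bootstrapping are already in the plan. Label any odds-ratio version as not testing additivity of risks.

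The cost is one sentence, a few lines of R and slightly lower apparent power to claim interaction. This change does not remove the smaller excess that comes from declaring interaction on any one of three intervals.

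### Three confidence intervals that include the null are read as absence of additive interaction, in a study sized only for the glucose main effect

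*Protocol*

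**What the plan says.** The statistical methods (unnumbered) assess the combined effect of GDM and the offspring's postnatal environment with three additive-interaction indices: RERI, AP and S. The decision rule has two branches. If the 95% intervals for RERI and AP include 0, and "the 95% CI of S included 1, it indicated no additive interaction"; "otherwise, there was an additive interaction". No third outcome is provided for data too imprecise to decide.

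The sample-size paragraph concerns the effect of high prenatal sugar on delayed language development. It states that "the incidence rate (p_1) of delayed language development in the group exposed to high prenatal sugar is 15"%, that "the relative risk (RR) is 2.0", with "a desired significance level (α) of 0.05" and power 0.90, and concludes that "both the exposed group and the control group require 160 individuals". After 10% for loss this becomes 356, with 360 planned. The Protocol gives no interaction effect size, prevalence of a poor nurturing environment, precision target or margin for the interaction analysis.

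**The concern.** An interval that includes the null shows that the data are compatible with no interaction. It does not show that there is none. Absence is supported only when the interval also excludes interactions large enough to matter, and the rule never asks for that.

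The gap matters more here because the study is sized for a main effect. Interaction contrasts draw on four exposure-by-environment cells, the smallest with few events, and are estimated much less precisely than a two-group comparison. Followed as written, the plan could lead the report to state that glucose exposure and nurturing environment do not interact when the data cannot say so. Both exposures are named in the project title, so readers will look for that statement.

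**Working it through.** **1. The plan's own figure.** The usual two-proportion formula (pooled variance under the null, two-sided 0.05, power 0.90) gives 161 per group for 30% against 15%, close to the stated 160. So 160 is reproduced if 15% is the unexposed risk. With 15% as the exposed risk, as worded, the comparison is 15% against 7.5% and needs 371 per group. That mismatch is a separate matter. Then 2 × 160 = 320 and 320 / 0.90 = 356. On either reading the calculation is for a main effect.

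**2. Inputs for the interaction check.**
- From the Protocol: the three-interval rule, 95% intervals, 360 planned, 10% loss.
- Derived: 360 × 0.90 = 324 complete children.
- Assumed, not in the Protocol: GDM 1:1, poor environment in 20%, 30% or 50%, no covariates, and the cell risks below.

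**3. Formulas** (odds-ratio scale, because the planned model is logistic):
- RERI = OR11 − OR10 − OR01 + 1
- AP = RERI / OR11
- S = (OR11 − 1) / [(OR10 − 1) + (OR01 − 1)]

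Intervals are by the delta method from a saturated logistic model, on the log scale for S.

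**4. One setting by hand.** Risks of 10/15/15/30% (neither exposure / GDM only / poor environment only / both) give odds of 0.1111, 0.1765, 0.1765 and 0.4286. Hence OR10 = OR01 = 1.588, OR11 = 3.857, and RERI = 3.857 − 3.176 + 1 = 1.68. The same risks give RERI = 1 on the risk-ratio scale (3 − 1.5 − 1.5 + 1), so the scale must always be stated.

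With 324 children and 30% poor environment, each GDM group has 162 children, 113.4 in a good and 48.6 in a poor environment. Expected events are 11.34, 17.01, 7.29 and 14.58. The log-odds variances (1/events + 1/non-events) are 0.0980, 0.0692, 0.1614 and 0.0980.

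Var(RERI) = 1.588² × (0.0692 + 0.1614) + 3.857² × 0.0980 + (3.857 − 3.176)² × 0.0980 ≈ 0.582 + 1.458 + 0.045 = 2.085, so SE ≈ 1.44.

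The interval is 1.68 ± 1.96 × 1.44, about −1.15 to 4.51. The simulated median interval is about −1.2 to 4.5.

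**5. Simulation of the full rule.** There were 40,000 cohorts per setting. The last column is the share in which all three intervals include the null, over the 20-50% prevalence range.

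| Risks (%) | RERI (odds-ratio scale) | n | Read as no interaction |
|---|---|---|---|
| 10/15/15/25 | 0.82 | 324 | 77-79% |
| 7.5/11/11/22 | 1.43 | 324 | 65-69% |
| 10/15/15/30 | 1.68 | 324 | 55-63% |
| 12/18/18/36 | 1.91 | 324 | 47-57% |
| 10/15/15/35 | 2.67 | 324 | 30-45% |
| 10/15/15/30 | 1.68 | 648 | 36-51% |
| 12/18/18/36 | 1.91 | 648 | 25-43% |

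The 648 rows (2 × 324) cover the reading that the 360 are the exposed group only. Over all three settings with RERI 1.4-1.9, the range at 648 is about 25-60%.

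**6. Sensitivity to the assumed risks.** A second simulation (20,000 cohorts per setting, n = 324) held the marginal relative risk for GDM at the Protocol's 2.0, with risks of 15% vs 7.5% or 30% vs 15%. The environment odds ratio in unexposed children was 1.5 or 2.0. The rule missed odds-ratio RERI 1 in 76-82%, RERI 2 in 46-68% and RERI 3 in 19-53%. The pattern is the same.

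**The case against.** The strongest reply is that no single miss rate can be attached to this plan, and that is right.

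- **Size of the interaction.** A reader might infer that the study would miss any large interaction at least half the time. The documents do not support this. They define no large interaction, and at odds-ratio RERI of about 2.7 the miss rate is 30-45%.
- **Sample size.** The figure of 324 is inferred. The 360 are planned for the cohort with abnormal blood sugar, which may mean exposed mothers only. The Protocol also describes a retrospective cohort whose size is not given. A larger total brings several settings below half.
- **Risks and prevalence.** The prevalence and effect of a poor environment are assumed. The risks in the main table imply marginal relative risks for GDM of about 1.55-1.80, not the planned 2.0. The second simulation answers that point without changing the conclusion.
- **Condition.** A reader might infer that a false negative conclusion is likely. That follows only if an interaction of moderate size really exists, which the documents cannot tell us.
- **Importance.** The title names two exposures but not their interaction. Low power for interaction is common and not itself an error, and published intervals would show the imprecision.

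All this limits the size of the claim and its severity. It does not rescue the rule: reporting an interval does not justify a written conclusion of absence that the interval cannot support.

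**Conclusion.** The point holds as a fault in the interpretive rule. The Protocol turns non-significance on three indices into a conclusion of no additive interaction, and its only sizing is for the glucose main effect.

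The miss rates illustrate the consequence and are not properties of the plan. They rest on the assumed cell risks, the 20-50% prevalence, 1:1 GDM, no covariates and a total of 324 or 648. In the main simulations they run from about 25% to 79%, depending on the interaction and the total. Excluding children with missing values, as planned, would reduce the usable number; covariate adjustment would usually lower precision further. Neither was simulated.

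The most direct evidence is the interval in step 4. It runs from below zero to about 4.5, so it would be read as no interaction while leaving a large one open. This should be corrected, but it affects one interpretive sentence and not data collection, estimates or intervals.

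**What to change.** In the paragraph on the combined effect of GDM and postnatal environment, replace the negative conclusion with: *there is no clear evidence of additive interaction; the result is inconclusive and each index is reported with its 95% CI.* Add that the sample was sized for the glucose main effect and not for interaction.

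Optionally, the plan could allow a claim of no material interaction when the whole interval of one named index lies inside a range set in advance. This is not needed to remove the fault.

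The cost is two sentences and a weaker negative conclusion. No further participants, data or software are needed.

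### The plan does not require variable selection to be repeated in each bootstrap replicate, so a nomogram validated as the text permits could look better than it is

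*Protocol*

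**What the plan says.** The Protocol (headed as a statistical analysis plan, version 1.0) has no numbered sections. The relevant text is in the paragraph on the regression models and nomogram and in the closing paragraph on software and significance levels.

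- **Models.** "The binomial logistics regression model and the lasso regression model were constructed by using the" rms and glmnet packages. The link between the lasso model and the nomogram is not stated.
- **Selection.** In the closing paragraph, "the selection criterion for the regression equation is set at a level of 0.05, and the exclusion level is set at 0.10".
- **Use.** "The total scores of each patient were calculated based on the nomogram for clinical prediction".
- **Performance.** "predictive performance of the nomogram was measured by concordance index (C index"). Correction for optimism is not mentioned.
- **Validation.** "Prediction models were validated by plotting calibration curves and using bootstrap method with one thousand replicate samples". Nothing says whether variable selection forms part of what is resampled.
- **Size.** The sample size paragraph plans 160 per group, 356 in total after allowance for loss, with 360 to be investigated. The candidate predictors are named only as families: sociodemographic, reproductive, environmental, scale and laboratory variables, with diet and exercise added in the opening description. Their number is not given.

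**The concern.** A model looks too good in its own data for two reasons: its coefficients were fitted there, and its variables were chosen there. A bootstrap that keeps the chosen variables and refits only their coefficients measures the first kind of optimism and misses the second. With few events and many candidates, the second can be the larger part.

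The plan specifies the entry and removal levels, the packages and the number of replicates. It leaves open the one choice that decides whether the bootstrap measures the whole optimism. An analyst could hold the variables fixed, follow the text to the letter, and report as internally validated a nomogram whose discrimination and calibration in new children would be clearly worse. Because the scores are offered for prediction in individual patients, that would mislead users. Decision-curve net benefit could be affected in the same way, but this was not computed.

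**Working it through.** **1. Number of events behind the nomogram.** The plan's sample size comes first. The pooled-variance formula for two proportions, two-sided alpha 0.05 (sidedness assumed) and power 0.90, with 15% against 30%, is

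n = [1.960·√(2·0.225·0.775) + 1.282·√(0.15·0.85 + 0.30·0.70)]² / 0.15² = 161 per group,

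against 160 stated (158 with unpooled variance). Then 320/(1 − 0.10) = 356, as stated. Expected events among 320 completers are 160·0.30 + 160·0.15 = **72**.

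The wording, however, attaches the figure to the exposed children: "delayed language development in the group exposed to high prenatal sugar is 15" per cent. Read literally with the plan's twofold risk ratio, the unexposed rate is 7.5% and the events number 160·0.15 + 160·0.075 = **36**. Which group the 15% belongs to is a separate matter; both event counts are carried forward.

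**2. Quantities compared.** For each simulated data set of n = 320, stepwise logistic regression (entry 0.05, removal 0.10) selects the model, which has apparent C index C_app. The bootstrap-corrected value is

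C_corr = C_app − mean over replicates of [C in the bootstrap sample − C of the same fitted model in the original sample].

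*Fixed* refits only the variables first selected. *Repeated* reruns the selection in each replicate. *True* is the C index of the selected model in 20,000 new subjects.

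**3. Main simulation.** Assumptions, not figures from the Protocol: 10, 20 or 30 independent candidates; three real predictors (exposure, plus two with log odds ratio 0.35 per SD); 60 data sets per setting and 40 bootstrap samples each. Data sets in which nothing was selected were dropped (0 to 6 of 60 per setting).

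| Candidates | Events | Apparent | Fixed | Repeated | True | Fixed − true | Repeated − true |
|---|---|---|---|---|---|---|---|
| 10 | 74 | 0.682 | 0.673 | 0.640 | 0.647 | 0.026 | −0.007 |
| 20 | 74 | 0.692 | 0.679 | 0.623 | 0.643 | 0.036 | −0.020 |
| 30 | 74 | 0.713 | 0.696 | 0.628 | 0.637 | 0.059 | −0.009 |
| 10 | 39 | 0.687 | 0.675 | 0.626 | 0.615 | 0.060 | 0.011 |
| 20 | 38 | 0.687 | 0.673 | 0.593 | 0.605 | 0.068 | −0.012 |
| 30 | 38 | 0.719 | 0.701 | 0.608 | 0.597 | 0.104 | 0.011 |

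The fixed-variable bootstrap removes only 0.009 to 0.018 of the apparent C (for example 0.682 − 0.673 = 0.009).

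Calibration slope across the six settings: fixed 0.92 to 1.10, repeated 0.54 to 0.77, true 0.40 to 0.81. The fixed-variable version therefore shows a slope near 1 for a model whose predictions are too extreme.

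**4. Sensitivity to the assumptions, about 70 events.**

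- More candidates, weak signal (60 data sets, 20 bootstraps). Fixed minus true: 15 candidates 0.633 − 0.590 = 0.043; 30 candidates with one real predictor 0.649 − 0.575 = 0.074; 30 with three 0.678 − 0.605 = 0.073; 50 with three 0.677 − 0.590 = 0.087. Repeated selection gave 0.574, 0.563, 0.602 and 0.571, each within 0.02 of the truth.
- Few candidates or stronger signal (40 to 80 data sets, 20 to 30 bootstraps). Eight candidates: 0.024 with three weak predictors (log odds ratio 0.35 to 0.40 per SD) and 0.009 with three stronger ones (0.5 to 0.8). Four stronger predictors (0.4 to 0.8; true C about 0.75): 0.014, 0.019 and 0.026 with 10, 15 and 30 candidates.
- A further run covering weak and stronger predictors gave 0.03 to 0.07 at about 72 events and about 0.08 at about 36. Repeating selection again came within about 0.02.

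The fixed-variable bootstrap was too high in every setting.

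**The case against.** **The text does not say the variables are held fixed.** A reader might infer that the bootstrap is planned for the finished nomogram only, and hence that the reported performance is bound to be inflated. The Protocol does not support this. It speaks of prediction models in the plural and is silent on the steps included. The sentence directly follows the one on the C index, so a corrected C index is a possible reading. The concern is therefore conditional on how the bootstrap is run.

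**The build sequence is not spelled out.** A reader might also infer that lasso screens the variables that enter the nomogram. The Protocol says only that both models were constructed. The 0.05 and 0.10 levels stand among the general conventions and could also serve the confounder-adjusted logistic regression described earlier. This stands as a caution. It does not remove the concern: the levels are set for the regression equation without exception, and the simulations used that rule alone.

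**This could be detail left for later.** That carries little weight here. The document is itself headed as a statistical analysis plan and goes down to packages and replicate count. A procedure that gives the wrong answer complies fully with what it says.

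**The size depends on assumptions.** This stands. With few candidates and strong predictors the excess is about 0.01. No single figure can be attached to this study until the candidate list is known.

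**Conclusion.** The concern holds in conditional form. The plan pairs data-driven selection with a 1000-replicate bootstrap, but does not require selection to be repeated in each replicate or the reported C index to be optimism-corrected. If only the already selected variables are refitted, which the text permits, the validated C index will be too high: by roughly 0.01 to 0.09 at about 70 events and by about 0.06 to 0.10 at about 36 to 38 events. In the six settings where calibration was examined, it looked better than it was.

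The direction was the same throughout. The size rests on assumed numbers of candidates (8 to 50), assumed predictor strengths, independent predictors and modest numbers of simulated data sets. Neither lasso nor net benefit was simulated, so no figure is claimed for them. This is a cheap improvement to the prediction part of the plan; it does not bear on the estimate of the exposure effect.

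**What to change.** Add to the paragraph on the nomogram:

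1. Which selection procedure produces the nomogram: the 0.05/0.10 entry and removal rule, lasso, or both. List the candidate predictors.
2. Every selection step that feeds the nomogram, including any tuning of the lasso penalty, is repeated from the full candidate list within each of the 1000 bootstrap samples.
3. The optimism-corrected C index and calibration slope are the headline performance measures, with the apparent values shown beside them.
4. The calibration plot shows the bias-corrected curve, and the decision curve shows optimism-corrected net benefit. The correction applies to these performance measures, not to individual predicted risks.

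No extra data or participants are needed. The cost is R programming, computing time and, most likely, a lower reported C index.
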